3.1. Description of Study Design

This is a single site, double blind placebo controlled study, which will assess the efficacy, safety, and steady state of Autologous Microbiome Transplant (AMT) cream in adults with AD. After providing informed consent, patients will be assessed for study eligibility at the screening visit, in which participants will consent to all of the study experiments separately. Subjects that withdraw from the study will be replaced. Eligible subjects will be randomized to receive either AMT cream or placebo in a 2:1 allocation ratio (AMT cream: placebo).

Subjects will be instructed to apply either the AMT or vehicle cream to both arms twice a day for seven days. Both subjects and clinical investigators will be blinded. Optional follow-up visits to assess clinical effect and steady state may occur at 1 and 4 hours after initial cream application if the subjects are willing to return at these time points. 4 days after the treatment visit, subjects will return to the clinic for fresh aliquots of the AMT and vehicle creams as well as to assess safety and clinical effect. Subjects will return to clinic after the seven day course of AMT or vehicle creams for clinical and safety assessments. Subjects will then be asked to return to the clinic 1 day after completion of the AMT or vehicle cream course for additional safety and clinical effect assessments. Subsequently, subjects will return for additional follow-up visits only if their lesional atopic dermatitis sites have not yet returned to baseline (*S. aureus* is no longer inhibited and *Staph species* from the AMT cream is zero). Up to 27 subjects will be recruited for this entire study. The duration of this study is approximately 2 months. We anticipate the entire study duration will be approximately 2 years total, and that it will take approximately 1 year to reach recruitment and enrollment goals for this study. The study flow diagram is provided in Figure 1.

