11.3. Participant Replacement

Participants who withdraw or are withdrawn will be replaced.

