13.4.2 Primary Analysis of Primary Endpoint(s)/Outcome(s)

Aim: The change in *S. aureus* abundance after 7 days of AMT cream by using skin swabs to determine the quantity of *S. aureus* using culture and qPCR.

For each AD subject, the abundance of *S. aureus* will be calculated using CFU counts from baseline (day 28) to Day 35 after 7 days of AMT cream application or placebo application. Comparisons of *S. aureus* reduction will be made between AMT cream and placebo subjects using a two-tailed t-test for independent samples with type II error rate of 0.2 and type I error rate of 0.05. The sample size will include 18 subjects in the AMT cream arm and 9 subjects in the placebo arm. Comparisons of AMT cream versus placebo cream will be reported as means, standard deviations, medians, and minimum and maximum. An intention-to-treat analysis will be conducted that includes all subjects who had at least one follow-up visit after intervention. A per-protocol analysis will also be conducted that includes all subjects who were compliant with the full intervention regimen with no major protocol violations.

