13.7 Sample Size Considerations

Number of *S. aureus* colonies will be a continuous variable, and change in *S. aureus* abundance will be measured as the absolute difference in number of colony-forming units at specified time points.

The sample size was calculated using G-Power Data Analysis software for a two-tailed t-test for independent samples, type II error rate of 0.2, and type I error rate of 0.05. The values used in the analysis were determined from our pilot study in which we quantified the reduction in *S. aureus* on the forearms of 5 atopic dermatitis patients twenty-four hours after treatment with a live microbiome transplant. Since the sample size was small in this study, we used the median and median average deviation as measures of central tendency. The median *S. aureus* present on the forearms of atopic dermatitis patients at baseline was 192.86 CFU/cm² with deviation of 191.86. We observed that a log-base 10 reduction by 1 of the number of bacteria present on the forearms to be a clinically significant reduction at 24 hours, with deviation of 21.42. Using $\mu_1 = 192.86$, $\mu_2 = 19.186$, and $\sigma_1 = 191.86$, and $\sigma_2 = 21.42$, the total sample size necessary to see this difference would be $n=24$ for an unequal allocation of subjects 2:1 in the treatment to placebo groups.

Assuming a drop-out rate of 20%, we propose a total $n=27$, with $n= 18$ in the treatment group and $n= 9$ in the placebo group. Assignment to treatment or placebo groups will be determined using simple randomization with an online random number generator.

This sample size is reasonable and practical within the scope of this funding mechanism and recruitment capabilities.

An intention-to-treat analysis will be conducted that includes all subjects who had at least one follow-up visit after intervention. A per-protocol analysis will also be conducted that includes all subjects who were compliant with the full intervention regimen with no major protocol violations.

14. Identification and Access to Source Data

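### Section 13.7: 24 evaluable subjects with 20% drop-out need 30 randomised, not 27, and the power inputs do not describe the change that is tested

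*Combined protocol and SAP*

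**What the plan says.** Section 13.7 uses a two-sided independent-samples t-test with alpha 0.05 and type II error 0.2. Its inputs are μ1 = 192.86 and μ2 = 19.186 CFU/cm², with σ1 = 191.86 and σ2 = 21.42. They rest on a five-patient pilot, for which "we used the median and median average deviation as measures of central tendency". From these, "the total sample size necessary to see this difference would be" 24 at 2:1. The next step is "Assuming a drop-out rate of 20%, we propose a total" of 27, split 18 and 9.

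The same section defines the outcome as a change: "abundance will be measured as the absolute difference in number of colony-forming units at specified time points". Section 13.4.2 compares the reduction between arms "using a two-tailed t-test for independent samples with type II error rate of 0.2 and type I error rate of 0.05".

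On withdrawals, Section 3.1 says "Subjects that withdraw from the study will be replaced" and Section 11.3 says "Participants who withdraw or are withdrawn will be replaced". On the total, Section 3.1 says "Up to 27 subjects will be recruited for this entire study" and Section 8.3 also gives 27, while Sections 4.2 and 13.1 each give up to 54.

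**The concern.** There are four faults, of unequal weight.

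1. Moving from 24 evaluable subjects to 27 randomised does not allow for 20% drop-out.
2. Replacement of withdrawals could make up the loss, but it cannot operate once a ceiling of 27 recruited subjects is reached. With 27 and 54 both in the text, a reader cannot tell whether 27 counts randomised subjects or completers.
3. The calculation uses a baseline level and an assumed 24-hour level, each with its own deviation. The primary test needs the SD of the change in each arm, and the document does not give it. The deviations are also not SDs.
4. The second mean does not follow from its own description as a one-log10 reduction.

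At stake is the type II error of 0.2 claimed in Sections 13.4.2 and 13.7. On the plan's own inputs it holds only if loss stays near 11% or withdrawals are replaced. For the quantity actually tested, it has not been shown at all.

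**Working it through.** **Reproducing 24.** All inputs are from Section 13.7.
- Difference: 192.86 − 19.186 = 173.674.
- Averaged SD: √((191.86² + 21.42²)/2) = 136.51.
- Standardised effect: d = 173.674/136.51 = 1.272.
- Two-sided noncentral-t power at alpha 0.05: 0.741 at 14:7 (21 subjects) and 0.802 at 16:8 (24 subjects). The plan's 24 is confirmed.

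**Drop-out step.**
- Required number randomised: 24/(1 − 0.20) = 30, that is 20 + 10.
- The common but incorrect shortcut, 24 × 1.2 = 28.8, does not give 27 either.
- Loss that 27 can absorb: 1 − 24/27 = 11.1%.
- Left after 20% loss: 27 × 0.8 = 21.6 (18 × 0.8 = 14.4 and 9 × 0.8 = 7.2).

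Power by the plan's method (d = 1.272):

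| Evaluable AMT:placebo | Power |
|---|---|
| 14:7 | 0.741 |
| 15:7 | 0.753 |
| 14:8 | 0.780 |
| 16:8 | 0.802 |
| 18:9 (full replacement) | 0.850 |
| 20:10 | 0.887 |

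**Replacement.** At 20% loss, 27 completers need 27/0.8 = 33.75, so 34 randomised; 24 completers need 30. Both exceed 27 and both fit within 54.

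**Second mean.** One log10 below 192.86 is 19.286. The entered 19.186 is one tenth of the deviation 191.86. With 19.286, d = 1.2715 and power at 16:8 is 0.801, so the slip has no practical effect.

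**Change endpoint.** Assumptions not in the documents: the stated deviations are SDs, the placebo mean and SD do not change, values are normal, and one baseline–follow-up correlation ρ applies in both arms.
- AMT SD of change: √(191.86² + 21.42² − 2ρ × 191.86 × 21.42).
- Placebo SD of change: 191.86 × √(2(1 − ρ)).
- Power is for the planned pooled t-test, simulated with 200,000 replicates per cell.

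| ρ | SD AMT | SD placebo | Power 18:9 | Power 16:8 |
|---|---|---|---|---|
| 0.3 | 186.6 | 227.0 | 0.53 | 0.48 |
| 0.5 | 182.1 | 191.9 | 0.60 | 0.54 |
| 0.7 | 177.5 | 148.6 | 0.69 | 0.63 |
| 0.8 | 175.2 | 121.3 | 0.75 | 0.68 |
| 0.9 | 172.8 | 85.8 | 0.82 | 0.76 |

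**Deviations treated as SDs.** This is a separate scenario on levels, not to be added to the one above. Rescaling under normality:
- If they are median absolute deviations: d = 1.272/1.4826 = 0.858, power 0.47 (16:8) and 0.52 (18:9).
- If they are mean absolute deviations: d = 1.272/1.2533 = 1.015, power 0.61 (16:8) and 0.67 (18:9).

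**Unequal SDs.** These are not counted as a shortfall. Simulated on the stated levels and SDs, the planned pooled t-test rejects in 0.86 (16:8) to 0.89 (18:9) of runs. Only a Welch test would fall to 0.60 to 0.66.

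**The case against.** The plan says without condition that withdrawals are replaced, and with full replacement power is 0.85, above target. On that reading the drop-out sentence is a slip with no consequence. This stands in part: under-powering from drop-out is possible, not demonstrated. It does not rescue the text, because Section 13.7 handles drop-out by inflating the sample size and never mentions replacement, and replacement at 20% loss cannot fit under a ceiling of 27.

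The 0.74 to 0.78 is an averaged-SD approximation. Simulating the pooled t-test on the stated unequal SDs gives 0.82 (14:7) to about 0.83 (15:7 and 14:8) after the same loss. That is true, but with equal means the same test then rejects in about 0.16 to 0.21 of runs, so those figures are not power at a 5% level. The averaged-SD method is also the one that reproduces the plan's 24.

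On level versus change, randomisation gives the arms equal expected baselines, so the difference in mean change equals the difference in mean follow-up level. Only the SD is open, and at ρ = 0.9 the 18:9 design reaches 0.82. This stands: 24 or 27 is not proven too small. The wording around 21.42 is also ambiguous and might describe the reduction, although it is entered as the SD of the group with mean 19.186.

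The rescaling of deviations assumes normality. With a mean of 192.86 and a deviation of 191.86, a normal model puts a material share of counts below zero. That scenario deserves little weight, and the caution extends to the other normal-based figures.

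**Conclusion.** The concern holds. The drop-out arithmetic is wrong on the plan's own numbers and needs no outside assumption: 30 are required, 27 covers 11.1% loss, and 20% loss without replacement leaves 21 to 22 evaluable with power of about 0.74 to 0.78 by the plan's method. The conflict between 27, 54 and the replacement rule is equally plain from the text. The 19.186 slip is real but has no effect on power.

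It is also certain that the power statement rests on levels and on deviations that are not SDs, while the test is on change. How much this costs is not known. The 0.53 to 0.82 range at 18:9 depends on a correlation the documents do not give, and the rescaled 0.52 to 0.67 depends on normality. The supported conclusion is that 80% power for the primary comparison is undocumented, not that it is absent. This should be fixed, and correcting the text is enough.

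**What to change.** - In Section 13.7, state either that 27 randomised allows about 11% drop-out, or that 20% drop-out leaves about 21 to 22 evaluable subjects with power of about 0.74 to 0.78 by the present method unless withdrawals are replaced.
- State whether inflation or replacement deals with drop-out, and whether 27 counts randomised subjects or completers. Align Sections 3.1 and 11.3 with that choice.
- Use one recruitment number in Sections 3.1, 4.2, 8.3, 13.1 and 13.7. If 54 is meant to cover screening or replacements, say so.
- Correct 19.186 to 19.286, or explain it.
- Restate power for the change that will be tested, over a stated range of SDs, and say what kind of deviation the pilot figures are. A log10 CFU change adjusted for baseline would be a better-behaved quantity; adopting it would also change Section 13.4.2 and is optional.

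The cost is a text revision. The planned 27 need not be raised. If the sponsor relies on replacement, more than 27 will be randomised, but the replacement rule already implies that. The downside is that the stated power becomes a range and looks less favourable.

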14.1. Source Data

Source documents and source data are considered to be the original documentation where subject information, visits consultations, examinations and other information are recorded. Documentation of source data is necessary for the reconstruction, evaluation and validation of clinical findings, observations and other activities during a clinical trial.

14.2. Access to Source Data

The site investigators and site staff will make all source data available to KAI, NIAMS, as well as to relevant health authorities. Authorized representatives as noted above are bound to maintain the strict confidentiality of medical and research information that may be linked to identified individuals.

15. Protocol Deviations

15.1. Protocol Deviation Definitions

Protocol Deviation – The investigators and site staff will conduct the study in accordance to the protocol; no deviations from the protocol are permitted. Any change, divergence, or departure from the study design or procedures constitutes a protocol deviation. As a result of any deviation, corrective actions will be developed by the site and implemented promptly.

Major Protocol Deviation (Protocol Violation) - A Protocol Violation is a deviation from the IRB approved protocol that may affect the subject's rights, safety, or well-being and/or the completeness, accuracy and reliability of the study data. In addition, protocol violations include willful or knowing breaches of human subject protection regulations, or policies, any action that is inconsistent with the NIH Human Research Protection Program's research, medical, and ethical principles, and a serious or continuing noncompliance with federal, state, local or institutional human subject protection regulations, policies, or procedures.

Non-Major Protocol Deviation - A non-major protocol deviation is any change, divergence, or departure from the study design or procedures of a research protocol that does not have a major impact on the subject's rights, safety or well-being, or the completeness, accuracy and reliability of the study data.

15.2. Reporting and Managing Protocol Deviations

The study site principal investigator has the responsibility to identify, document and report protocol deviations as directed by the study Sponsor. However, protocol deviations may also be identified during site monitoring visits or during other forms of study conduct review. Upon determination that a protocol deviation has occurred, the study staff will notify the site Principal Investigator and complete a Protocol Deviation form. Protocol deviations, as determined by the PI, will be reported to the appropriate review bodies including the IRB, SO, and FDA, who will review and approve the action plan that will be implemented as a result of the protocol deviation.

16. Ethical Considerations and Compliance with Good Clinical Practice

16.1. Statement of Compliance

This clinical study will be conducted using good clinical practice (GCP), as delineated in *Guidance for Industry: E6 Good Clinical Practice Consolidated Guidance*, and according to the criteria specified in this study protocol. Before study initiation, the protocol and the informed consent documents will be reviewed and approved by the IRB and FDA. Any amendments to the protocol or to the consent materials will also be approved by the IRB and FDA before they are implemented.

16.2. Informed Consent Process

The consent process will provide information about the study to a prospective participant and will allow adequate time for review and discussion prior to his/her decision. The principal investigator or designee listed on the *FDA 1572* will review the consent and answer questions. The prospective participant will be told that being in the trial is voluntary and that he or she may withdraw from the study at any time, for any reason. All participants (or their legally acceptable representative) will read, sign, and date a consent form before undergoing any study procedures. Consent materials will be presented in participants' primary language. A copy of the signed consent form will be given to the participant.

The consent form will be revised when important new safety information is available, the protocol is amended, and/or new information becomes available that may affect participation in the study.

